1 SUMMARY OF THE PROTOCOL

1.1 SYNOPSIS

Title:	Lifestyle Intervention Clinical Trial for the Remission of Type 2 Diabetes Mellitus in Primary Care (CREDOenAP) [Ensayo clínico de intervención estilo de vida para la reversión de Diabetes Mellitus tipo 2 en Atención Primaria (CREDOenAP)]
Grant Number:	N/A
Study Description:	Intervention program with intensive lifestyle counseling, added to standard pharmacological treatment subsequently adjusted according to clinical needs and outcomes. The intervention will last 6 months and consists of biweekly in-person and telephone visits. Patients will follow a personalized dietary plan with carbohydrate restriction, based on the recommendations of the American Diabetes Association; engage in moderate and accessible physical activity; implement circadian rhythm regularization; and receive psychological counseling and support.
Objectives*:	
Primary objective:
 
To quantify the proportion of Type 2 Diabetes (T2DM) remission among participants without evidence of absolute insulinopenia enrolled in the lifestyle intervention program (CREDOenAP) at the end of the program (6 months).
 
Secondary objectives:
 
- To quantify the percentage of T2DM remission among participants in the lifestyle intervention program (CREDOenAP) one year after completion of the program (18 months).- To determine the nutritional, physical activity, and quality-of-life patterns of participants in the CREDOenAP program before, at the end of the intervention and one year after (18 months).- To assess anthropometric, metabolic, and imaging markers of cardiovascular risk in participants in the CREDOenAP program before, at the end of the intervention (6 months) and one year after completion (18 months).

Endpoints^{*}:

Primary Endpoint:

- Percentage of participants achieving type 2 diabetes remission at 6 months, defined as HbA1c <6.5% after 6 months of intervention and at least 3 months without antidiabetic medication. HbA1c will be determined through fasting blood analysis (minimum 8 hours).
- Percentage of participants achieving T2DM remission at 6 months, defined as fasting venous plasma glucose <126 mg/dL after 6 months of intervention and at least 3 months without antidiabetic medication. Fasting glucose will be measured through venous blood analysis after a minimum 8-hour fast.

Secondary Endpoints:

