A consensus panel of ADA experts has developed and agreed upon criteria and definitions for the terms reversal, partial remission, complete remission, and prolonged remission of type 2 diabetes (T2DM) (*Riddle et al., 2021*). Diabetes remission is defined as achieving glycemic levels (fasting plasma glucose and HbA1c) below the minimum thresholds required for a T2DM diagnosis, i.e., fasting plasma glucose <126 mg/dL or HbA1c <6.5%.

To meet remission criteria, participants must be free from any pharmacological therapy or procedures (e.g., gastric band adjustments) for at least 3 months.

Lifestyle and Type 2 Diabetes

The WHO Global Action Plan for the prevention and control of chronic diseases, such as type 2 diabetes (T2DM), hypertension, obesity, and at least 13 obesity-related cancers (*CDC, 2017; Secretan et al., 2016*), recommends focusing efforts on addressing harmful lifestyle factors, including tobacco and alcohol use, physical inactivity, and unhealthy diet (*World Health Organization, 2013*).

According to the ADA, diabetes self-management education and support are essential to achieve therapeutic goals for type 2 diabetes (T2DM). These measures include medical nutrition therapy, physical activity, counseling for smoking cessation, and psychosocial support (*Committee ADAPP, 2021*).

Type 2 Diabetes – Current Management and Proposed Improvements

Although nutrition and physical activity are placed at the center of international guidelines for diabetes management (ADA/EASD), in clinical practice the pharmacological approach is clearly predominant. Economic data indicate that the cost of diabetes is increasing each year, with the largest share attributed to pharmaceutical expenditures. (*Crespo et al., 2015*). Currently, reversal and remission of type 2 diabetes (T2DM) are not considered primary treatment goals, with management focused on maintaining metabolic values within target ranges.

In the context of Spain, most interventions follow a pharmacological approach, representing high-cost measures for the healthcare system. The CREDOenAP intervention could provide evidence on lifestyle-focused strategies as a therapeutic pillar for T2DM remission, and evaluate their feasibility and effectiveness in primary care. Potential T2DM reversal through lifestyle intervention could have economic and organizational impact by reducing pharmaceutical costs and decreasing the number of medical visits associated with diabetes management.

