5.1 INCLUSION CRITERIA

The inclusion criteria for patient recruitment in this study are as follows:

1. Signed informed consent.
2. Men and women aged 18–80 years, inclusive.
3. Confirmed diagnosis of T2DM according to recognized diagnostic criteria (*Association, 2021*)
4. Most recent recorded hemoglobin A1c (HbA1c) > 6.5%.
5. Body Mass Index (BMI) greater than 27 kg/m².

Individuals considered eligible for recruitment must meet all of the above inclusion criteria and be able to comply with the activities described in the intervention process.

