5.2 EXCLUSION CRITERIA

The exclusion criteria for this study are as follows (meeting any of these criteria precludes participation):

1. Failure to meet the diagnostic criteria for T2DM in the screening laboratory tests.
2. Being dependent for basic activities of daily living (Barthel score ≤ 90 points).
3. Lack of willingness to cooperate with the follow-up of the lifestyle intervention plan.
4. Presence of serious or terminal comorbidities significantly worsening short- to medium-term prognosis (active cancer, terminal chronic diseases, myocardial infarction within the last 6 months, acute heart failure or NYHA stage ≥ III, etc.).
5. History of ketoacidosis.
6. Presence of criteria or potential autoimmune insulinopenia (abnormal C-peptide, anti-GAD+ antibodies, pattern of basal and/or glucose-stimulated hypoinsulinemia).
7. Cognitive impairment.
8. Weight loss exceeding 5 kg in the past 6 months.
9. Significant changes in physical activity and/or dietary patterns in the past 6 months.
10. History of eating disorders.
11. History of substance abuse.
12. History of severe psychiatric disorders.
13. Pregnancy or intention to become pregnant within the study period.

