8 STUDY ASSESSMENTS AND PROCEDURES

8.1 ENDPOINT AND OTHER NON-SAFETY ASSESSMENTS

To evaluate the effectiveness of the CREDOenAP intervention on the different health indicators defined in the objectives, various variables will be collected.

Sociodemographic Variables

- **Sex:** dichotomous variable according to biological sex (Male/Female).

- **Age:** age at study entry.
- **Living situation:** current living arrangement (Lives alone / Lives with others).
- **Socioeconomic level:** determined using the individual health insurance card (TSI) based on the pharmaceutical copayment level. Copayment is calculated according to each individual's income and employment status. Based on the copayment contribution, individuals are categorized into four socioeconomic levels:
 - **Very low:** TSI 001, exempt from copayment. Includes individuals receiving minimum insertion income, active insertion income, guaranteed citizen income, exhausted unemployment benefits, or non-contributory pensions.
 - **Low:** TSI 002 (10% copayment) and TSI 003 (40% copayment). Population with annual income < €18,000.
 - **Medium:** TSI 004 (50% copayment) and TSI 006. Population with annual income €18,000–€100,000 or individuals in administrative mutual schemes.
 - **High:** TSI 005 (60% copayment). Population with annual income > €100,000.

Clinical Variables

- **Year of T2DM diagnosis:** year of T2DM registration in eCAP.
- **Main comorbidities:** the primary active diagnoses recorded in eCAP will be obtained and corroborated with the participant.

Primary Outcome Variables

All primary outcome variables will be measured, calculated, and recorded at study baseline, at the end of the intervention, and 12 months after the intervention.

- **Presence of T2DM remission** (according to ADA consensus definition, (Riddle *et al.*, 2021)):
 - **Glycated hemoglobin (HbA1c):** T2DM remission will be considered if HbA1c is < 6.5% after 6 months of intervention and at least 3 months without antidiabetic medication. HbA1c will be determined by blood analysis after a minimum of 8 hours of fasting (Association, 2021)
 - **Fasting plasma glucose:** T2DM remission will be considered if fasting venous plasma glucose is < 126 mg/dL after 6 months of intervention and at least 3 months without antidiabetic medication. Fasting plasma glucose will be measured by venous blood analysis after a minimum of 8 hours of fasting (Association, 2021)

Secondary Outcome Variables

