Potential participants will receive an invitation to take part in the study during their last medical consultation (in person or by telephone) by their physician, nurse, or the principal investigator. They will then be scheduled for a screening visit with a member of the research team, following completion of the screening blood test. Patients will be informed of the necessary requirements for the laboratory tests (fasting status and first morning urine sample) as well as the location where they will be carried out (extraction and laboratory areas of each primary care center).

Screening and Study Inclusion Visit

During this visit, eligibility criteria will be assessed to determine whether patients meet the study selection requirements. Participants who fulfill the criteria will receive a detailed explanation of the study objectives and the implications of participation. They will be provided with the study information sheet and, if they agree to participate, will sign an informed consent form for data collection throughout the study. If consent is obtained, a physical examination (anthropometric measurements) will be performed, sociodemographic variables will be recorded, and participants will complete the questionnaires assessing quality of life, physical activity, nutritional status, and lifestyle habits (including substance use). Additionally, appointments will be scheduled for all participants to undergo the imaging test (Carotid ultrasonography).

Laboratory Tests

Blood and urine analyses will be performed at three different time points during the study: at baseline, at the end of the intervention, and 12 months after completion of the intervention. These analyses do not involve any additional procedures, as they are part of the routine clinical practice for monitoring and follow-up of all patients with type 2 diabetes mellitus (T2DM) in primary care. No requests, extractions, or analyses will be conducted outside of standard clinical care. The laboratory tests will include: Complete blood count, HbA1c, Creatinine, Glomerular filtration rate, GOT (AST), GPT (ALT), GGT, Ionogram, Lipid profile (Total cholesterol, HDL, LDL,

Triglycerides, Apo B100), Fasting insulin, Anti-GAD antibodies (only at baseline), Urine: sediment and albumin/creatinine ratio.

Imaging Diagnosis: Carotid ultrasonography

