9.2 SAMPLE SIZE DETERMINATION

Based on the primary variable of the intervention, the percentage of T2DM remission, the required sample size has been calculated to observe statistically significant differences. This variable will be coded dichotomously. A total of 120 volunteers (60 per arm) will be recruited for the study. Accepting an alpha risk of 0.05 (5%) and a beta risk of less than 0.2 in a two-sided test, at least 52 subjects in the control group and 52 subjects in the intervention group would be required to detect as statistically significant a 20% difference between two proportions (primary endpoint: T2DM remission). For the control group, the expected remission rate ranges from 0 to 5%, whereas in the intervention group, it is expected to be at least 25%. The remission rates have been benchmarked against previous studies (Lean et al., n.d.). An estimated loss to follow-up rate of 15% has been considered.

Given the estimated 15% loss to follow-up, the sample size has been increased to 60 participants instead of 52. This ensures that the statistical power of the analysis will be preserved.

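### An untreated patient with fasting glucose below 126 mg/dL can be enrolled and then counted as a glucose-defined remission without any change

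*Protocol*

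**What the plan says.** **Entry.** Section 5.1 asks for a confirmed diagnosis, BMI above 27 and "Most recent recorded hemoglobin A1c (HbA1c) > 6.5" per cent, with no age limit on the recorded value. The only criterion that refers to fresh blood is exclusion 1 in section 5.2: "Failure to meet the diagnostic criteria for T2DM in the screening laboratory tests". Section 8.1 places the screening visit "following completion of the screening blood test". No criterion requires current antidiabetic medication, and none sets a minimum fasting glucose.

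**Endpoint.** The Synopsis, section 3 and section 8.1 define remission separately for each marker. The glucose version in the Synopsis is "defined as fasting venous plasma glucose <126 mg/dL after 6 months of intervention and at least 3 months without antidiabetic medication". Section 8.1 repeats it: "T2DM remission will be considered if fasting venous plasma glucose is < 126 mg/dL after 6 months of intervention and at least 3 months" off medication. The HbA1c version has the same form: "T2DM remission will be considered if HbA1c is < 6.5% after 6 months of intervention and at least 3 months" off medication. Section 8.1 has remission recorded at baseline as well, but no rule says what to do with a participant who already qualifies then.

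**Thresholds.** Section 2.2 gives the limits as "fasting plasma glucose <126 mg/dL or HbA1c <6.5" per cent, joined by an or.

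**Planning.** Section 9.2 assumes a 20-point difference: "For the control group, the expected remission rate ranges from 0 to 5" per cent, at least 25% with the intervention, 52 evaluable and 60 recruited per arm.

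**The concern.** Eligibility can rest on one marker while remission is scored on the other. If a patient is untreated and the two markers disagree at entry, one primary definition may already be satisfied on the day of randomisation, apart from the passage of time. That patient needs only to stay the same to be counted as a remission at 6 months and, under the 18-month glucose endpoint in the Synopsis and section 3, as maintaining remission.

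Two things are at stake. The stated primary objective is to quantify the proportion in remission, and that percentage would include people whose status the programme did not change. The between-arm comparison on which the sample size rests would also be diluted, because the same people raise both arms.

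**Working it through.** **Step 1: is the route open?** Take a patient on no antidiabetic drug with HbA1c 6.8% and fasting glucose 118 mg/dL, who meets the other criteria.

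- Inclusion 4: 6.8% is above 6.5%, so met.
- Exclusion 1: HbA1c is in the diabetic range at screening. Nothing in 5.1 or 5.2 asks for both markers to be raised, so the patient is not excluded.
- Glucose definition: 118 is below 126 and the patient is drug-free, so the marker and drug-free terms are met at T0.

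The route is open on the text. A footnote to the assessment table in section 8.1 itself foresees discordant HbA1c and glucose.

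**Step 2: the second route.** Take an untreated patient with an older recorded HbA1c of 6.9%, now 6.3%, and glucose 128 mg/dL. This patient enters and already meets the HbA1c terms only if (a) the screening sample is not itself taken as the most recent recorded HbA1c, and (b) glucose alone satisfies exclusion 1. The protocol settles neither, so this route is conditional. A patient with both markers below threshold is excluded.

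**Step 3: reproduce the plan's figure.** For rates pc and pt, with p̄ their mean and n per arm:

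power = Φ{[(pt − pc) − 1.96·√(2p̄(1−p̄)/n)] / √([pc(1−pc) + pt(1−pt)]/n)}

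For 5% vs 25% at n = 52: (0.20 − 1.96 × 0.0700)/0.0672 = 0.933, so power is 82.5%. The same formula needs 49 per arm for 80%. The planned 52 is slightly conservative and meets the stated beta.

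**Step 4: effect of patients who qualify at T0.** Assume a share x of each arm meets the glucose definition at T0 and stays there, the rest remit at the planned rates, and glucose-defined remission is the variable compared. Then each arm's rate is x + (1−x) × planned rate, and the difference is (1−x) × planned difference. The protocol gives no x; the values below are assumptions.

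Example, x = 5%, 5% vs 25%: control 0.05 + 0.95 × 0.05 = 9.75%; intervention 0.05 + 0.95 × 0.25 = 28.75%; difference 19.0 points. Power: (0.19 − 1.96 × 0.0773)/0.0750 = 0.512, giving 69.6%.

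Observed rates and power at 52 per arm:

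| Planned rates | x = 0 | x = 5% | x = 10% |
|---|---|---|---|
| 5% vs 25% | 82.5% | 9.75% vs 28.75%: 69.6% | 14.5% vs 32.5%: 58.3% |
| 0% vs 20% | 93.7% | 5% vs 24%: 79.4% | 10% vs 28%: 65.2% |
| 0% vs 25% | 98.0% | 5% vs 28.75%: 91.0% | 10% vs 32.5%: 81.0% |

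The middle row keeps the 20-point difference at the bottom of the control range, although section 9.2 expects at least 25% with the intervention.

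**Step 5: control rate against plan.** If control remission among the others is 5%, any x above 0 takes the observed control rate past the planned ceiling. If it is 0%, that happens only once x exceeds 5%. Among 60 per arm, x = 5% is 3 people and x = 10% is 6.

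**The case against.** **The analysis uses baseline values.** Sections 9.4.1 to 9.4.3 adjust for the baseline outcome or baseline HbA1c. This stands for the model estimates, and the power figures above are for unadjusted proportions. Adjustment does not take such a patient out of the reported remission percentage, nor out of the risk differences and numbers needed to treat.

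**Some analyses are not touched.** Section 9.4.2 names change in HbA1c as primary, and that analysis is unaffected. The 18-month model in section 9.4.3 defines remission by HbA1c only, so the glucose route does not reach it. Both points stand. The glucose endpoints at 6 and 18 months in the Synopsis and section 3 remain exposed.

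**The affected group is probably small.** It must be untreated for 3 months, discordant on the markers, and stay so. Section 5 describes poor glycaemic control, and the Synopsis describes a programme added to standard drug treatment. This is fair, but no figure is given.

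**Power looks worst at the top of the control range.** True: at 0% vs 25% it is still 81% with x = 10%. The table therefore spans the planned range.

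**Stronger readings.** A reader might infer that the remission comparison becomes uninterpretable, or is biased towards the intervention. The documents do not support this: randomisation spreads these patients over both arms, so the effect on the comparison is dilution. A reader might also infer that any outdated HbA1c lets in a patient already in HbA1c-defined remission. That ignores exclusion 1 and the screening blood test, and holds only under both conditions in step 2.

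**Conclusion.** The concern holds in a limited form. The criteria admit untreated patients with HbA1c above 6.5% and glucose below 126 mg/dL, and the glucose definition counts them as remissions without change. The consequences are an inflated glucose-defined remission percentage and an arm difference shrunk by the factor (1−x). HbA1c-defined remission is affected only through the conditional second route.

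The size is unknown because the protocol gives no x. On the assumptions that these patients persist in both arms and that glucose-defined remission is compared as a simple proportion, x = 5% costs about 13 points of power at 5% vs 25% (82.5% to 69.6%) and about 7 points at 0% vs 25% (98.0% to 91.0%). If x is close to zero, the practical effect is negligible. The gap is in the wording whatever its size, and the entry part cannot be repaired once patients are enrolled.

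**What to change.** 1. In sections 3 and 8.1, state that a participant who meets a remission definition at T0 (marker below threshold and no antidiabetic medication in the previous 3 months) cannot be counted as a responder on that definition at 6 or 18 months. State whether such participants leave the denominator for that definition. Leaving them out is sound because the rule uses only information from before randomisation. Alternatively, require both markers below threshold for remission; the planned rates in section 9.2 would then need rechecking against the stricter definition.
2. In section 5.1, state that the HbA1c in inclusion 4 is the value from the screening or baseline sample. This closes the conditional second route.

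The cost is mainly wording. The schedule of activities already places HbA1c and glucose before randomisation and a medication review at the first assessment; the 3-month medication history must be recorded explicitly. The downside is a slightly smaller denominator for the glucose definition, or a few candidates lost from about 2,800 registered patients. For scale, x = 5% would leave 52 × 0.95 = 49.4 per arm, and 49 per arm still gives 80.1% power at 5% vs 25%.

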5.2 EXCLUSION CRITERIA

The exclusion criteria for this study are as follows (meeting any of these criteria precludes participation):

1. Failure to meet the diagnostic criteria for T2DM in the screening laboratory tests.
2. Being dependent for basic activities of daily living (Barthel score ≤ 90 points).
3. Lack of willingness to cooperate with the follow-up of the lifestyle intervention plan.
4. Presence of serious or terminal comorbidities significantly worsening short- to medium-term prognosis (active cancer, terminal chronic diseases, myocardial infarction within the last 6 months, acute heart failure or NYHA stage ≥ III, etc.).
5. History of ketoacidosis.
6. Presence of criteria or potential autoimmune insulinopenia (abnormal C-peptide, anti-GAD+ antibodies, pattern of basal and/or glucose-stimulated hypoinsulinemia).
7. Cognitive impairment.
8. Weight loss exceeding 5 kg in the past 6 months.
9. Significant changes in physical activity and/or dietary patterns in the past 6 months.
10. History of eating disorders.
11. History of substance abuse.
12. History of severe psychiatric disorders.
13. Pregnancy or intention to become pregnant within the study period.

5.3 LIFESTYLE CONSIDERATIONS

Since this study involves a behavioral intervention aimed at changing patients' lifestyle, participants must commit to following the recommendations upon which the intervention protocol is based. The restrictions and recommendations (detailed in Appendix 1) are as follows:

- Adherence to a low-carbohydrate Mediterranean diet. Participants should reduce or avoid the following:

- Processed and ultra-processed foods
- Added sugars and sweeteners (e.g., sugar, honey, syrups)
- Starchy foods (e.g., bread, pasta, rice, potatoes, legumes, cereals)
- High-fructose fruits (e.g., bananas, grapes, dates, tropical fruits)
- Fruit juices and sugar-sweetened beverages (including “zero-calorie” drinks)
- Fried foods (frying is discouraged; the only recommended oil is extra virgin olive oil, consumed raw)
- Avoid alcohol consumption
- Avoid tobacco use
- Daily physical activity:
 - Recommended 10,000 steps per day
 - Strength training (progressive and individualized): During the first two weeks, at least one hour of walking per day is recommended. Strength exercises will then be gradually introduced (e.g., two sets of 5–10 squats). Weightlifting routines may be added according to individual tolerance.
- Healthy circadian habits:
 - Maintain regular sleep schedules
 - Wake up between 6:00 and 8:00 a.m.
 - Sun exposure for 15 minutes (preferably between 7:00 and 9:00 a.m.)
 - Go to bed before 11:00 p.m.
 - Sleep approximately 8–9 hours per night
- No use of pharmacological treatments or supplements for weight or appetite control is allowed during the study.

